Phase I/II Trial Examining Dose-per-fraction Escalation using Intensity Modulated Radiation Therapy in the Treatment of Prostate Cancer

A University of Wisconsin Tomotherapy Group Study

University of Wisconsin Participants:

Study Chair [name]., Ph.D.

Radiobiology [name]., D.Sc.

Statistician [name].

M.D. Anderson Cancer Center Orlando:

Institutional PI: [name].

Wayne State University:

Institutional PI: [name].

Medical College of Wisconsin:

Institutional PI: [name].

INDEX

	Schema
1.0	Background
2.0	Objectives
3.0	Selection of Patients
4.0	Registration Procedures
5.0	Treatment Plan
6.0	Measurement of Effect
7.0	Study Parameters
8.0	Statistical Considerations
9.0	Records to be Kept
10.0	References
Appendix I	Patient consent form
Appendix II	Fox Chase Bowel/Bladder Toxicity Questionnaire
Appendix III	International Erectile Function Questionnaire
Appendix IV	The Spitzer Quality of Life Index (SQLI)
Appendix V	Acute and Late Toxicity Data Sheet
Appendix VI	Eligibility Checklist
Appendix VII	Partin Tables

[figure not shown]
STUDY CHAIR

[name]., Ph.D.
Clinical Science Center
[name]
[name]
[contact]

Protocol Information Network Contact Person

[name] – [contact]
[name]- [contact]

SCHEMA

* As described in Section 5.1, institutions joining the study after Level I is filled will treat two patients at Level I before proceeding to enter patients at the level that the overall trial is currently accruing to.

^a 50 evaluable patients will be enrolled per dose/fraction level and followed for toxicity. These 50 patients will be analyzed for dose-per-fraction escalation and fraction-per-week escalation. Additional patients may be enrolled in Levels one and two while waiting for higher dose level data and toxicity information to mature per Section 4.0

^b An additional 100 patients will be enrolled at the MTS (Maximum Tolerated Schedule) level in addition to the 50 patients already accrued at that level

1.0 BACKGROUND

1.1 Introduction

[figure not shown]
Prostate cancer is the most common non-skin cancer in American men, resulting in over 30,000 deaths annually in this country. Optimal treatment for localized, potentially curable, prostate cancer has not been determined, but radiation therapy has an established and major role in the management of localized disease, a role supported by evidence that disease control rates comparable to radical prostatectomy are achieved but with less toxicity.

The probability of achieving biochemical control after radiation therapy is related to the pre-treatment PSA, tumor grade and local stage, with PSA and grade being the most important factors. For example, patients with pre-treatment PSAs of less than 6 ng/ml and Gleason scores less than or equal to 6, have 5-year biochemical control rates of 87%, whereas patients with PSAs 10 – 20 ng/ml and Gleason scores of 7 have control rates of only 45%. Radical prostatectomy outcomes are also influenced strongly by these same pre-treatment predictors.

It has long been felt that one of the most important factors limiting the success of radiation therapy has been the inability to deliver adequate radiation dose without producing unacceptable toxicity. More recently, however, innovations in cancer imaging, radiation treatment planning and treatment delivery technology have created opportunities for safe dose escalation.

1.2 The rationale for dose escalation

[figure not shown]
Retrospective studies have indicated a substantial dose response for prostate cancer. Hanks et al (1) examined Patterns of Care data and found actuarial local recurrence rates of 37% for Stage C patients treated to less than 60 Gy, 36% for doses of between 60-64.9 Gy, 28% for 65-69.9 Gy and 19% for doses of 70 Gy or more. Similarly, Perez et al (2) found 38% local recurrences for doses less than 60 Gy, 20% for doses between 60 and 70 Gy and only 12 % for doses of 70 Gy or greater. More recently, a number of retrospective studies (3-7) and one randomized trial (8) have demonstrated superior PSA recurrence-free survival when doses higher than 70 Gy are delivered, at least for intermediate or higher risk patients (**Figure 1**). These results and the unsatisfactorily high rates of disease persistence in intermediate to higher risk patients after conventional dose radiation therapy (66-70 Gy) provide a strong rationale for the delivery of higher than conventional radiation doses.

**Figure 1.**

Tumor control probabilities for “intermediate risk” patients. Data derived from 4 published series (Fowler, unpublished)

When delivered with conventionally planned techniques, however, doses higher than 70 Gy are associated with higher complication risks (9). It has now become clear that 3D conformal radiotherapy demonstrates better than historically expected tolerance of normal tissues to higher doses (6, 10, 11) but complication rates, particularly rectal bleeding, can still be substantial. Various analyses suggest that the total area of rectal wall exposed to greater than 60 or 70 Gy predicts the rate of rectal bleeding or more severe grade 4 complications such as ulceration (Figure 2). Therefore, the implementation of intensity modulated radiotherapy, with its ability to further reduce rectal irradiation, should further reduce toxicities, as has indeed been reported by Zelefsky et. al. (12).

Prostate_Rectal Complics

**Figure 2.** Grade 2 or higher rectal complications versus rectal area receiving higher than specified radiation doses. A summary of 6 clinical trials. (13)

With these advancements in delivery precision for radiation to a planned treatment volume, the minimizing of daily uncertainties regarding patient setup reproducibility and the change of position of the prostate within the pelvis because of rectal and/or bladder filling takes on a significant role. Currently at the University of Wisconsin Department of Radiation Oncology, we are using an optically guided 3D-ultrasound target localization system (SonArray™, Zmed, Inc., Ashland, MA) to correct daily for these misalignments at the time of treatment to within 2 mm along each axis (Tome, in press, 2001). As an alternative, the implantation of small metal seeds into the prostate to serve as fiduciaries during daily portal imaging has also proven reliable as a means of localizing the prostate

In addition, it has been demonstrated that the use of a rectal balloon catheter can immobilize the prostate and facilitate localization on port films potentially allowing tighter margins for the treatment volume. Also, the lateral and posterior aspects of the rectal wall are displaced out of the high dose region by the rectal balloon, which should offer the potential for significant rectal sparing (14, 15).

1.3 Hypofractionated Radiotherapy for prostate cancer

While the above-described physical improvements in dose delivery have permitted larger total doses of radiation to be delivered to the prostate without undue toxicity, the added number of fractions of radiation required have produced an increasing burden in terms of cost, utilization of resources and inconvenience to the patient. Some dose escalation regimens currently exceed 43 treatments and exceed 8 weeks in duration. Evidence has emerged over the past two years, however, of a unique prostate cancer radiobiology that may offer the opportunity to dramatically improve the efficiency and safety with which radiation therapy is delivered.

Conventional fractionation schemes employing fraction sizes of 1.8 – 2.0 Gy are based upon the premise that tumors typically are less responsive to fractionation than are late-responding normal tissues. The α/β ratios are one measure of fractionation response, with low ratios (high β 's) being more associated with late responding normal tissues, indicating greater repair between fractions with an accompanying greater relative sparing with small fraction sizes than for tumors with their higher α/β ratios. Under these conditions, an improved therapeutic ratio is achieved with multiple small fractions.

In contrast, prostate cancers appear to be better able to repair radiation injury than late responding normal tissues. This is probably related to the very slow growth fractions and growth rates typical for prostate cancer. Growth fraction (or average cell cycle time) has often been associated with fractionation response, with slowly proliferating normal tissues (and some slowly proliferating tumors) generally displaying strong fractionation responses (low α/β ratios). This relationship has been demonstrated for melanomas (16) and for some sarcomas (17), for example. In the case of prostate cancer, there is ample evidence for slow proliferation, based both upon direct measurement of potential doubling times and labeling indices (18) and upon analysis of the kinetics of rising PSA during tumor recurrence (19). Recent analyses of clinical tumor response data have argued for a low α/β ratio for prostate cancer as well (20, 21). Brenner and Hall (20), for example, analyzed dose response data for both external beam radiation and I-125 brachytherapy data and derived a very low α/β ratio of 1.5 Gy for prostate cancer. Duschene and Peters (21) argue in analogous fashion that the α/β ratio for prostate cancer may be more similar to that expected for late responding normal tissue than for the typical, more rapidly proliferating tumor.

Our own analysis of tumor control versus dose response for external beam and brachytherapy also indicates a very low α/β ratio of 1.49 (95% CI of 1.25 to 1.76) (22), significantly lower than the ratio of 3 expected for most late responding normal tissues.

Under these unusual conditions, in which the α/β ratio of the tumor is lower (the radiation repair capacity is higher) than that for the limiting normal tissue, a new paradigm is created in which it becomes advantageous to use larger fractions; in other words, to use hypofractionation, rather than the traditionally larger number of smaller fraction size radiation treatments employed when treating most other tumor types. In fact, the old way of fractionating would be the least efficient method. Using the linear quadratic model, one can predict that it should be possible to improve the ratio of tumor control to normal tissue toxicity (the therapeutic ratio) for prostate cancer by using hypofractionation.

Although begun before this unique prostate cancer radiobiology was understood, a relatively large clinical trial has already been carried out using hypofractionation for prostate cancer. Cleveland Clinic investigators have carried out a trial of hypofractionation consisting of 28 fractions of 2.5 Gy each for a total dose of 70 Gy (23). Intensity modulated radiotherapy (IMRT) and daily pretreatment ultrasound-based prostate localization were employed to improve treatment precision and reduce radiation dose to the rectum. These investigators are now reporting 2-year follow-up in which rectal and bladder toxicities are no greater and likely lower than previously experienced with conventional fractionation of 2 Gy per day to 76 Gy using conventional 3D conformal radiotherapy techniques (Mohen, in press, 2002). Furthermore, these early results appear to indicate better tumor control (PSA recurrence-free survival) than was seen with standard fractionation, although follow-up is too short to reach definitive conclusions regarding tumor control.

1.4 Biomarkers of Prostate Cancer Radiation Response

There is increasing evidence that cancers can have molecular alterations that render them poorly responsive to radiation therapy and that are associated with a significant proportion of treatment failures. Preliminary findings indicate, for example, the status of certain biomarkers, such as p53, and Bcl-2, correlate with success or failure of radiation therapy treatment for prostate cancer (30-36) but more such studies are needed to further identify markers and to define the strength of these correlations with treatment outcome, particularly in favorable or intermediate risk patients, the type of patient most frequently diagnosed today and the type treated in this present study.

We will therefore study certain biomarkers in the diagnostic biopsy specimens of patients treated on this protocol. These biomarkers have been selected based upon prognostically useful prevalences in early to intermediate risk prostate cancer and based upon their having pathways linked to radiation response. We will immunohistochemically measure the levels of p53, Bcl-2, and Ki-67 in pre-treatment diagnostic biopsy specimens from patients enrolled on this study and will analyze correlations between these markers and clinical outcomes (freedom from biochemical and metastatic failure) in univariate and multivariate fashion, taking conventional prognosticators such as stage, grade and PSA into account.

1.5 Study Rationale

Hypofractionation Trial

The purpose of this study is to examine the clinical feasibility of using IMRT combined with daily pretreatment prostate localization to deliver increasingly hypofractionated treatment courses. Progressively larger fraction sizes will be delivered in a phase I design based on both acute and long-term tolerances to the treatment. The dose-per-fraction escalation design utilizes schemas that maintain an isoeffective dose for late effects, while predicting that tumor control will actually improve. A natural consequence of these constraints is that the total dose of radiation that can be delivered over an entire course of therapy must decrease as the dose delivered with each fraction increases.

Late effects increase with fraction size and total dose delivered whereas acute toxicities increase with total dose and as overall treatment time is shortened. Excessive shortening of overall treatment time could be a natural consequence of hypofractionation if treatments continue to be delivered daily even as fraction size is increased. Thus, any hypofractionation trial design must guard against an unacceptable increase in acute toxicities by considering whether treatments can continue to be delivered daily (5 days per week), as is generally the case with conventional treatment, or whether treatment frequency needs to be reduced. The proposed study will therefore initiate treatment at each fraction size level with only 4 fractions per week and will only increase to 5 fractions per week if tolerated.

The delivery of fewer, larger fractions of radiation, if proven effective and safe, would result in significant cost saving and a more efficient use of resources. In addition, patients would be spared the burden of undergoing the 40 or more treatments required in most current, conventionally fractionated, dose escalation regimens. Time and effort saved could be applied to upgrading pretreatment verification of patient and organ position.

Biomarker Study

The purpose of the biomarker study is to identify tumor biomarkers useful in predicting which prostate cancers are or are not likely to respond to radiation therapy. If successful, this proposed study will define biomarkers that are clinically useful in predicting response to radiation therapy in favorable-to-intermediate risk patients. This will provide insight into the mechanisms of resistance to radiation therapy and will potentially allow future therapies, including novel biologic/molecular therapy approaches, to be prospectively individualized to optimize clinical outcome.

Participation in the tissue study is optional and is also dependent on the availability of tissue. The decision to participate in Biomarker study will not affect nor influence any patient treatment according to the remainder of this hypofractionation protocol. Subjects agreeing to tissue study participation will sign a consent indicating this decision.

2.0 OBJECTIVES

2.1 To evaluate acute and long-term tolerances to dose-per-fraction escalation in the treatment of prostate cancer using optimized treatment delivery that employs IMRT, daily rectal balloon displacement, and transabdominal ultrasound localization of the prostate.

2.2 To clinically evaluate local tumor control and biochemical progression-free survival and metastasis-free survival.

2.3 To immunohistochemically measure the levels of p53, Bcl-2, and Ki-67 in pre-treatment diagnostic biopsy specimens from patients enrolled on this study and will analyze correlations between these markers and clinical outcomes (freedom from biochemical and metastatic failure) in univariate and multivariate fashion, taking conventional prognosticators such as stage, grade and PSA into account.

3.0 SELECTION OF PATIENTS

- Histologically proven adenocarcinoma of the prostate.
- Stage ≤ T2b disease, as defined by 1997 AJCC classification
- Predicted risk of lymph node involvement (by standard nomograms) of 15% or less (24), OR histologically negative pelvic nodes
- Gleason score ≤ 7
- No evidence of distant metastasis
- Age 18+
- Informed consent signed in accordance with institutional protocol
- Pretreatment evaluations must be completed as specified in Section 7.0.
- ECOG performance status 0-1
- No previous or concurrent cancers, other than localized basal cell or squamous cell skin carcinoma, unless continually disease free for at least 5 years
- No prior pelvic irradiation, prostate brachytherapy, or bilateral orchiectomy
- Gonadotropin-releasing hormone agonist (GnRH-a) use permitted (maximum of 6 months duration). Anti-androgen therapy permitted concurrently with GnRH-a.
- No previous or concurrent cytotoxic chemotherapy
- No radical surgery or cryosurgery for prostate cancer
- The absence of any co-morbid medical condition which would constitute a contraindication for radical radiotherapy
- The absence of serious concurrent illness of psychological, familial, sociological, geographical or other concomitant conditions which do not permit adequate follow-up and compliance with the study protocol.
- No current use of anticoagulation therapy, other than aspirin.

4.0 REGISTRATION PROCEDURES

Patients can be registered only after eligibility criteria are met. Patients must have signed informed consent. Patients are registered prior to any protocol treatment by faxing the registration page to [contact] and calling [contact]. The UW data managers will verify eligibility, assign a case number, dose level, and confirm the number of fractions per week.

Patients will be enrolled on the highest available dose level open to accrual. If the highest dose level has reached full accrual with insufficient follow-up for further dose-per-fraction escalation, accrual will take place at one dose level lower, if one exists.

Enrollment will be permanently closed when the maximum tolerated dose per fraction is reached or when the dose per fraction escalation is complete.

5.0 TREATMENT PLAN

5.1 General

The accrual goal will be 50 evaluable patients in each of the three dose levels. An additional 100 patients will be enrolled at the determined MTS (Maximum Tolerated Schedule). An exception to this accrual target will be made for any new institutional participant joining the trial after Level I accrual has been completed, in which case that institution will treat two patients to completion at Level I (22 fractions, 5 treatments a week) irrespective of the current hypofractionation level the overall trial currently is treating. After two such patients have been treated, these institutions will then be allowed to accrue to the Level currently open in the trial. In addition, if the highest dose level has reached full accrual with insufficient follow-up for further dose-per-fraction escalation, accrual will take place at one dose level lower. As a result, patients will be enrolled on the highest available dose level open to accrual.

Both acute and late toxicities will be monitored and will dictate subsequent accrual. The level of acute toxicity observed will dictate the number of fractions delivered per week, whereas the level of late toxicities will determine both whether accrual to a dose-per-fraction level is continued and whether escalation to the next dose-per-fraction level is allowed. The escalation rules are as stated in 5.2 and 5.3, with the statistical rationale being described in Section 8. Given this study design, predicting the overall number of patients accrued is difficult. Assuming we are able to complete Levels 1-3 without dose limiting toxicity and taking into account the possibility of further enrollment into a lower dose level per escalation rules, the enrollment could be as high as 400 patients.

5.2 Dose-per fraction escalation

Escalation to the next higher dose-per-fraction level (or the accrual of an additional 100 patients to the MTS) will only be allowed when there is at least 20 patient years of follow-up and at least 5 patients have been followed for at least 12 months. A rate of 20% grade 2 or higher late rectal toxicity per patient follow-up year will be considered dose limiting. Late toxicities will be scored > 90 days from completion of therapy. The statistical rationale and methodology for this dose-per-fraction escalation strategy is described in section 8.0. Of note, statistical fluctuations in measured toxicity rates could occasionally lead to an initial over- or underestimation of these rates. Therefore, cumulative toxicity rates will be updated every 6 months throughout the life of the protocol and will be utilized according to the rules stated above.

The expected accrual timetable, the proposed dose-per-fraction and total fraction levels, and patient accrual goals for this phase I/II trial are shown in Table 1 below.

Table 1: Fraction size dose escalation protocol

Level	Approx. Interval (mo)	Dose per Fx (Gy)	# Fxs	# pts	Treatments per week	Total dose (Gy)	Equiv. dose (Gy)
I	1-15	2.94	22	50*	3 ← 4 → 5	64.68	82.6
II	16 - 30	3.63	16	50	3 ← 4 → 5	58.08	85.1
III	31 - 45	4.3	12	50	3 ← 4 → 5	51.6	85.5

* See section 5.1 for exceptions. Patients are initially treated 3 or 4 times per week, with this treatment frequency subsequently increasing, decreasing or remaining the same based upon the number of acute toxicities observed, as described in Section 5.3.

All of the three above levels are predicted to be approximately isoeffective for late effects at BED_3 equals approximately 128 Gy₃. In other words, each of these dose-per-fraction levels would be predicted to produce about the same level of late toxicity, all other factors such as high dose rectal wall volume remaining constant. Furthermore, the above schemas are all predicted to produce the same late toxicity as the fractionation regimen successfully piloted by Kupelian and Mohan(23) of 2.5 Gy times 28 fractions.

An additional **100** patients may be accrued to the MTS if toxicities observed in the first patients at the level are within the limits specified in the standard escalation rules.

The accrual intervals for each level stem directly from the escalation rules that will be followed, which are described in detail in Section 8. While not shown, predicted tumor control at each of the levels can be extrapolated from the fitted model of actual tumor control data in Figure 1, combined with the increased biologically effective doses calculated for each dose-per fraction-level as shown in the last column of Table 1. Such calculations are theoretical, but provide the rationale to believe that the hypofractionation schemas proposed here may produce increasingly better tumor control with fewer fractions.

5.3 Number of fractions per week and acute toxicities

Acute toxicities, as defined in section 5.6, will be assessed to determine the number of fractions at the given fraction size that can be delivered per week. The first 10 patients enrolled at each fraction size level will receive either 3 or 4 fx/week, depending upon how well tolerated previous fractionation levels and weekly treatment frequencies were tolerated. Acute toxicities will be reanalyzed and acted upon if necessary for subsequent groups of 10 patients. For toxicities observed within the first 10 patients at each hypofractionation level, $\geq 20\%$ acute grade 3 or higher GI or GU toxicity will constitute a threshold toxicity level and will dictate a decrease in frequency of treatment by one treatment per week for the next 10 patients to be treated at that hypofractionation level. If $> 20\%$ acute toxicity is also observed in this second group of 10 patients, treatment frequency will be further reduced by one treatment per week for all remaining patients in that hypofractionation level. If excess toxicity is not seen **after changing to a** lower treatment frequency, then all remaining patients in that hypofractionation level will continue to be treated at that frequency.

- If exactly 20% of patients within the first group of ten patients at any hypofractionation level experiences acute grade III or higher GI or GU toxicity, then the next ten patients at that hypofractionation level will remain at the same weekly frequency of treatment,

subject to the usual treatment frequency de-escalation if excess acute toxicities are observed.

- If < 20% of the first ten patients within the level experience this threshold toxicities, then the subsequent patients will be treated at the next higher treatment frequency sublevel, again subject to de-escalation if excess acute toxicities are observed.
- For an individual patient who develops acute toxicity at or above the Grade 3 level, that patient will be placed on treatment break for one week and treatments will then resume at the next lower treatment frequency. For example, if that patient was being treated 4 times per week at the time grade 3 or higher acute toxicities developed, he would subsequently be treated 3 times per week. A longer treatment break can also be prescribed if the treating physician feels that it is clinically indicated.
- At any hypofractionation level, a reduction in treatment frequency to two fractions per week will be allowed for a given patient if that patient experiences a threshold or higher toxicity at 3 fractions per week.
- Acute toxicities will be scored from the start of treatment through 90 days post completion of radiation therapy. Late radiation toxicities will be scored from 90 days post completion of radiation therapy.

5.4 Target volume and rectal dose limits.

Target volume. The GTV will generally be defined to include the entire prostate gland as visualized on CT scan. Seminal vesicles will be included in the GTV for 75% of the prescription dose if the estimated risk for seminal vesicle involvement is $\geq 15\%$ (24). For situations where there is less than 15% risk of seminal vesicle involvement, the base of the seminal vesicles may be included in the GTV at the discretion of the treating physician. The CTV will represent the same volume as the GTV plus a 0.3 cm margin in all dimensions except at the prostate-rectal interface, for which a margin of between 0 and 0.3 cm can be used. The PTV will include the CTV with a margin to account for patient and organ motion. This margin beyond the CTV is expected to range between 0 – 0.4 cm depending upon the accuracy of the daily pretreatment localization method used. Some form of pretreatment prostate localization must be used, either transabdominal ultrasound, Megavoltage CT (using Tomotherapy) or fiducial markers. Block margins will be chosen to provide adequate coverage of the PTV with no more than 10% dose heterogeneity across the PTV. At least 95% of the PTV must receive the prescription dose or higher. All planning will be carried out using an intensity modulated radiation therapy treatment planning system and delivered with an IMRT capable LINAC or with the tomotherapy machine.

Rectal dose limits. The rectal wall volume (outer minus inner) will be contoured for a total length of 11-12 cm beginning at approximately the inferior-most portion of the ischial tuberosities and extending to at least one cm above the most cranial extent of the treatment fields. Rectal wall percent volumes versus dose, as derived from the dose volume histogram, should be kept at or below values given in Table 2 whenever possible:

Table 2: Rectal Percent Limits vs. Dose

Level	Dose per Fx (Gy)	# Fxs	Total dose (Gy)	Dose (Gy)					
				30	35	40	50	55	60
I	2.94	22	64.68	-	-	37%	25%	-	13.5 %
II	3.63	16	58.08	-	38%	32%	19%	12%	-
III	4.3	12	51.6	40%	-	26.5%	12%	-	-

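### The weekly-frequency rules conflict on the starting frequency and on the action at exactly 2 of 10, and set no floor for cohort reductions

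*Combined protocol and SAP*

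**What the plan says.** - **Starting frequency.** Section 1.5 says the study will "initiate treatment at each fraction size level with only 4 fractions per week and will only increase to 5 fractions per week if tolerated". Section 5.3 says "The first 10 patients enrolled at each fraction size level will receive either 3 or 4 fx/week", the choice resting on how earlier levels and frequencies were tolerated. The note under Table 1 in 5.2 agrees with 5.3: "Patients are initially treated 3 or 4 times per week".
- **Range.** Table 1 lists 3, 4 and 5 treatments per week for all three levels, centred on 4. Its note refers to 5.3 for how the frequency moves.
- **Cohort reductions.** In 5.3, a rate of at least 20% in the first ten patients "will dictate a decrease in frequency of treatment by one treatment per week for the next 10 patients". If the second ten exceed 20%, "treatment frequency will be further reduced by one treatment per week for all remaining patients in that hypofractionation level". No lower limit is stated.
- **Exactly 20%.** A bullet in 5.3 keeps the next ten patients at the same frequency when exactly 20% of the first ten are affected. Another bullet steps the frequency up when fewer than 20% are.
- **Individual reductions.** A later bullet says "a reduction in treatment frequency to two fractions per week will be allowed for a given patient", if he has threshold toxicity at 3 per week.
- **New sites.** For an institution joining after Level I accrual is complete, 5.1 says "that institution will treat two patients to completion at Level I (22 fractions, 5 treatments a week".

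**The concern.** Weekly frequency is one of the two things this trial escalates. The schema footnote says the 50 patients per level are analysed for fraction-per-week as well as dose-per-fraction escalation. The person who confirms a patient's frequency therefore needs one answer from the protocol.

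As written, the starting frequency depends on which section is read, and one possible result in the first ten has two opposite consequences. The reductions can also take a whole cohort to a frequency that Table 1 does not list and that 5.3 otherwise mentions only for a single patient. Acute toxicity results at a level would then be hard to attribute to a planned schedule.

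**Working it through.** The plan gives no operating characteristics for the frequency rule, so there is no stated figure to reproduce.

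**1. Starting frequency.** Section 1.5 allows one value (4); 5.3 and the Table 1 note allow two (3 or 4). The criterion in 5.3 is tolerance at previous levels. Level I has no previous level, so the criterion cannot choose between 3 and 4 there.

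**2. Reachable cohort frequencies.** Apply 5.3 to every outcome from 0 to 10 in the first and second groups of ten. Each path reads first ten, second ten, remaining patients.

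- Start of 4: 4-3-2, 4-3-3, 4-5-4, 4-5-5. If exactly 2 of 10 means no change, also 4-4-3 and 4-4-4.
- Start of 3: 3-2-1, 3-2-2, 3-4-3, 3-4-4. If exactly 2 of 10 means no change, also 3-3-2 and 3-3-3.

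Under both readings a cohort can reach 2 per week from either start, and 1 per week from a start of 3. The remaining patients are 50 − 20 = 30 per level. For Level I (22 fractions) the course lasts 22/4 = 5.5 weeks at 4 per week, 22/2 = 11 at 2 and 22/1 = 22 at 1.

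**3. Chance of both reductions.** Let X be the number affected out of 10, binomial with true rate p: P(X ≥ k) = Σ C(10, j) p^j (1 − p)^(10 − j), summed over j = k to 10. The second cut needs more than 20%, so X ≥ 3. The first needs X ≥ 2 (reading A, the at-least-20% sentence) or X ≥ 3 (reading B, the exactly-20% bullet). With the same p in both groups, the chance is P(X ≥ 2) × P(X ≥ 3) under A and P(X ≥ 3)² under B. The documents give no acute Grade 3+ rate, so p is an assumed range.

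| p | P(X ≥ 2) | P(X ≥ 3) | P(X = 2) | Both cuts, A | Both cuts, B |
|---|---|---|---|---|---|
| 5% | 0.0861 | 0.0115 | 0.0746 | 0.0010 | 0.0001 |
| 10% | 0.2639 | 0.0702 | 0.1937 | 0.0185 | 0.0049 |
| 20% | 0.6242 | 0.3222 | 0.3020 | 0.2011 | 0.1038 |
| 30% | 0.8507 | 0.6172 | 0.2335 | 0.5251 | 0.3810 |

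From a start of 3, the first cut alone leaves the Table 1 range. Its probability is 26.4% at p = 10% and 62.4% at p = 20% under A, or 7.0% and 32.2% under B.

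**4. Exactly 2 of 10.** Two of ten is 20%. It meets the at-least-20% condition for a decrease and also the exactly-20% condition for no change. From the table, its probability is 19% at p = 10% and 30% at p = 20%.

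**5. New sites.** Section 5.1 states 5 per week without referring to the frequency Level I reached under 5.3. If Level I ended at 5, the two agree. If it ended below 5, 5.3 keeps the remaining patients of that level at the lower frequency while 5.1 assigns 5.

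**The case against.** Several points on the other side have force.

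- **Table 1 defers to 5.3.** Its note says the frequency moves as 5.3 describes, so the table need not be a cap, and the schema diagram is not available to settle the matter. This stands as far as it goes. It does not explain why 5.3 mentions 2 per week only for an individual, or whether a cohort at 2 or 1 was intended.
- **Section 1.5 is background.** The two operative passages agree on 3 or 4. That limits the conflict but does not remove it, and Level I still has no criterion for choosing.
- **Registration is central.** A reader might infer that sites would assign different frequencies to the same patient. Section 4.0 has the coordinating centre's data managers confirm the fractions per week, so that inference is not supported. The data managers still need a single rule.
- **The probabilities assume a constant rate.** Section 1.5 says acute toxicity rises as treatment time shortens. Slower treatment should then lower the rate in the second group, so the chances of both cuts are upper-end figures. At a true rate of 5% the chance is negligible.
- **The 5.1 rule is a declared exception.** It applies after Level I accrual is complete, Table 1 refers to it, and 5 per week is within the listed range. A reader might infer an outright contradiction with 5.3, or that new sites would use a frequency already found too toxic. Nothing in the documents says Level I settled below 5, so the conflict is only conditional. The exception is, however, worded for the accrual target and the level, not for the frequency rule.
- **Acute toxicity cannot close a level.** This could be read as an omission. Section 5.1 deliberately gives frequency to acute toxicity and accrual to late toxicity, and the DSMB in 8.4 can recommend action.
- **A level started at 3 can never reach 5.** This could be read from the one-step increase. Section 5.3 also says later groups of ten will be reanalysed and acted upon if necessary, so the claim is not established.

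**Conclusion.** The point holds as an inconsistency in stated operating rules. Three parts follow from the text alone: the starting frequency differs between 1.5 and 5.3, exactly 2 of 10 has two opposite consequences, and the cohort reductions have no floor and can leave the 3-to-5 range of Table 1. The fourth, between 5.1 and 5.3, arises only if Level I settled below 5.

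The practical size depends on an acute Grade 3+ rate that the documents do not give. Over assumed rates of 5% to 30%, the chance of two successive cuts runs from about 0.1% to 53% under reading A and from about 0.01% to 38% under reading B. The conflict at exactly 2 of 10 is more likely than a double cut at low rates: 19% against about 2% (reading A) at a true rate of 10%.

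A reader might also infer that the Maximum Tolerated Schedule is itself defined by frequency, so that the 100-patient expansion would inherit an unlisted schedule. The documents do not define it that way. Section 8.1 defines the maximum tolerated dose-per-fraction by late rectal toxicity.

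**What to change.** Reconcile 1.5, 5.1, 5.3 and Table 1 so that one rule, preferably set out as a small table of every reachable path, states:

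1. the starting frequency at each level and the criterion for it, including Level I;
2. the action when exactly 2 of the first 10 patients are affected;
3. the range of frequencies a cohort may receive, kept distinct from what a single patient may receive and the same in 5.3 and Table 1;
4. what follows if the threshold is exceeded at the lower end of that range.

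In 5.1, cross-refer the new-site frequency to the frequency Level I reached under 5.3. Which frequencies and thresholds apply is for the investigators to decide; none is proposed here.

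The cost is protocol wording, with no extra patients or procedures. The downside is that a level may pause for review when the lowest listed frequency is reached.
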